#### **10.3.4 Central Data Repository**

Once the EMR data is merged with project data, personal identifiers, such as patient name, medical record number, full address (excluding zip code) and phone number, will be removed from the dataset and stored as a separate encrypted dataset. An individual's study ID will be the 'crosswalk' linking this master file containing PHI to the coded analytic dataset. Access to

the master file will be limited to the BEDAC and BMC staff listed on this application who will be trained in handling confidential data.

The master file will be destroyed upon study completion (June 2022). Once treatment outcomes are verified by BMC staff, date of birth and treatment dates will be transformed into analytic variables (e.g. age at diagnosis, days to first treatment, # of days on chemotherapy, days to hormone therapy, etc.), removed from the dataset and stored as a separate encrypted dataset, linked only by the crosswalk file, as described above.

The central data repository will be maintained on a BMC secure, HIPAA compliant server for the purposes of matching the REDCap and Aunt Bertha data prior to de-identification for analyses. Good data management procedures to protect the electronic files will be followed as described above.

All patient information for data analysis will be transferred to the TRIP Central Data Repository to be stored on BMC virtual servers via secure, HIPAA compliant data transfer methods, with all data encrypted. Uploads into the repository will be protected using secure socket layering encryption technology. Web-forms and accompanying database will be stored on secure servers professionally maintained by the Boston Medical Center IT group, stored behind the BMC 'firewalls.' Access to data systems will be controlled by usernames and passwords and restricted to study personnel.

Datasets in SAS software will be stored on a HIPAA compliant network maintained by the BU Office of Information Security. Systems will be backed up incrementally and backups maintained offsite. All data will be stored in a HIPAA compliant manner and data storage techniques will be reviewed biannually by BU IT staff. Specific procedures, which have been approved by our institution review board (IRB) and used successfully in prior research, include protecting participant confidentiality as follows:

- Data will be stored in a centralized data warehouse located within the BU/BMC data centers and security procedures will be consistent with those already followed for EHR data.
- All project staff will sign an oath of confidentiality to ensure their understanding of the terms of confidentiality required.
- Only project staff will have access to the system via a secure name and password.
- All reports and publications will preserve the subjects' anonymity.

### **10.3.5 Protecting Confidentiality**

This requires that identifying information (name, address, date of birth, social security or Medicare numbers) not be used as the final sources of identification for participants. Compliance of regulatory documents and study data accuracy and completeness will be maintained through an internal study team quality assurance process. Confidentiality throughout the trial is maintained by utilizing only HIPAA compliant systems to collect and store Patient Health Information.

The major risk of the trial is loss of confidentiality. Because of the nature of the information, data collected on the patients requires the presence of patient identifiers, until the final analytic file is complete for analysis. When a patient record is started in REDCap, the platform automatically assigns an identifying number to the patient. This number will then become the identifier of records for each participants (for all relevant data) once the data is coded for analytic purposes at the end of the study.

## **10.4 Data Safety Meetings**

### **10.4.1 Participants**

The TRIP team members and site investigators will participate in the Data and Safety Meetings. The meetings will be chaired by one of the lead PIs. For any decisions or resolutions requiring a vote, the four lead PIs, six site clinical advisors, and the biostatistician will be considered voting members. A **quorum for voting** will consist of at least three PIs and two additional voting members.

### **10.4.2 Frequency**

The initial data and safety meeting will occur prior to the roll out of the intervention to discuss the protocol and establish guidelines for data review, and monitoring the study. Once the intervention is underway, the team will convene as often as necessary, but at minimum once a year (months 21, 33, 45, 57) to examine the enrollment data, review study progress and safety data, and discuss factors that might impact continuation of the study as designed.

### **10.4.3 Data for Meetings**

Responsibilities for data reporting are as follows:

- The data manager, in collaboration with the biostatistician will prepare detailed reports on enrollment, follow-up, data capture from the registry and from Aunt Bertha, monthly Quality Assurance reports and cancer care variables
- The project manager will report on protocol adherence and violations
- The data manager will report on data confidentiality and any reported adverse events from the database

### **10.4.4 Structure of Meetings**

Meetings will be open to invited members of the study team. If needed, a closed session may follow to allow discussion among lead PIs, site clinical advisors, project manager(s), biostatistician, and the data manager. Voting members and the quorum are described above.

#### **10.4.5 Addressing Data and Safety Concerns**

If issues are identified with data management or with participant safety or confidentiality, changes in the study protocol, data management, or data collection and maintenance will be discussed at the meeting and reflected in the minutes.

### **10.5 Reporting**

#### **10.5.1 Responsibility**

It is the responsibility of the lead PIs to ensure that safety and data quality reports are prepared in a timely manner and submitted to the relevant IRB and sponsor(s). The project manager will assist with this and maintain copies of all reports in the regulatory binder.

#### **10.5.2 Data and Safety Meetings Minutes**

The minutes of the Data and Safety Meetings will be prepared by an assigned committee member and reviewed by the lead PIs. If required by the BMC/BU Medical Campus IRB, the minutes will also be sent to the IRB either after each meeting or on an annual basis for re-certification. The summary reports will be sent to each site investigator and filed with the BMC IRB.

#### **10.5.3 Safety Definitions**

##### **10.5.3.1 Serious Adverse Events (SAEs):**

As this is a study monitoring the timeliness and quality of medical care in women with breast cancer, we do not anticipate any serious adverse events. Events that may occur during the course of the study of patients with cancer including treatment related events or death will not be considered SAEs for the purpose of reporting unless they are related or probably related to participation in the study.

##### **10.5.3.2 Adverse Events (AEs):**

The study has designed and instituted measures to preserve participant confidentiality. In particular, the study aims to prevent breach of data and loss of confidentiality, should any of the information in the registry, Aunt Bertha, or the secure central data repository become stolen or inadvertently become public. The study will also monitor for other possible AEs such as loss of contact with participants, misdirection or navigator error in participants' appointments or transfer of care, or unauthorized disclosure of personal information.

##### **10.5.3.3 Unanticipated Problems (UPs):**

An unanticipated problem is defined as an event, experience or outcome that meets all three of the following criteria:

- is unexpected; AND
- is related or possibly related to participation in the research; AND
- suggests that the research places subjects or others at a greater risk of harm (including physical, psychological, economic, or social harm) than was previously known or recognized.

*Possibly related* means there is a reasonable possibility that the incident, experience, or outcome may have been caused by the procedures involved in the research. *Unexpected* means the nature, severity, or frequency of the event is not consistent with either:

- The known or foreseeable risk of adverse events associated with the procedures involved in the research that are described in (a) the protocol-related documents, such as the IRB-approved research protocol, any applicable investigator brochure, and the current IRB-approved informed consent document, and (b) other relevant sources of information, such as product labeling and package inserts; OR

The expected natural progression of any underlying disease, disorder, or condition of the subject(s) experiencing the adverse event.

#### **10.5.4 Safety Event Reporting**

The Principal Investigator at BMC/BU Medical Campus will report Unanticipated Problems, SAEs, safety monitors' reports, and Adverse Events to the BMC/BU Medical Center IRB in accordance with IRB policies:

- Unanticipated Problems occurring at any participating site involving a fatal or life-threatening event will be reported to the IRB within 2 days of the investigator learning of the event.
- Unanticipated Problems occurring at any participating site not involving a fatal or life-threatening event will be reported to the IRB within 7 days of the investigator learning of the event.
- Reports from the safety monitor with recommended changes after review by the lead PIs will be reported to the IRB within 7 days of the investigator receiving the report.
- Adverse Events (including Serious Adverse Events) will be reported in summary at the time of continuing review, along with a statement that the pattern of adverse events, in total, does not suggest that the research places subjects or others at a greater risk of harm than was previously known.
- Reports from the safety monitor with no recommended changes will be reported to the IRB at the time of continuing review.

#### **10.5.5 Protocol Deviations**

The lead PIs will ensure all protocol deviations are reported to the NIH and BUMC IRB according to the applicable regulatory requirements.

### **10.6 Quality Assurance of Data**

To ensure reliability of data entry and collection, a 15% random sample of completed manually abstracted data elements will be reviewed by the TRIP study team to ensure outcomes and covariates were accurately abstracted and data entered. This data will be checked for quality by TRIP study personnel by accessing the Electronic Health Records on a hospital-issued device using BMC's VPN services, or viewing remotely through BMC's instance of Zoom using BMC's VPN services. Any differences identified will be documented and brought to the data manager for resolution. If the data manager cannot resolve the differences identified, they will be reviewed by the Clinical Adjudication Panel, which will meet as needed through BMC's instance of Zoom. The Clinical Adjudication Panel will be composed of a rotating membership selected

from the six site clinical advisors, the study personnel who conducted the initial abstraction and the cross-check, the project manager, and the data manager.

Quality assurance reports will be prepared by the data manager on a quarterly basis and reviewed by the Principal Investigators. The reports will inform the Principal Investigators about missing, invalid, inconsistent data on selected key variables. The statistician, in collaboration with the data manager on the project will oversee preparation of the reports. The reports will contain a summary of monthly accrual and cumulative accrual, a summary of key characteristics of the study participants, a summary of the completeness and quality of data.

Quality assurance will involve engaging in good data management activities. Procedures that include checking the integrity of data storage (facilitate in collaboration with BMC IT) and examining frequency distributions statistically (in collaboration with the BU School of Public Health) to look for data anomalies such as an excessive number of 'no response' or problems with any skip patterns included in the REDCap registry forms will be in place.

## **10.7 Stopping Rules**

The study has no stopping rules.

## **11 Study Records Retention**

This study will follow recommended Boston Medical Center retention guidelines requiring that study records be retained for at least seven years after completion of the study. As the study team is requesting a waiver of consent, retention of consent forms will not be required. Records will be preserved in their original form (hardcopy, electronic or other media) and saved as an electronic back-up copy whenever possible. All records will be made accessible for inspection and copying by authorized individuals.

## **12 Statistical Plan**

### **12.1 Study Hypotheses**

Our main hypothesis is that the TRIP intervention will result in timelier breast cancer treatment that is more concordant with guidelines, compared with historical control data. We also hypothesize that the integrated TRIP intervention will be implemented across each of the six study sites.

### **12.2 Sample Size Determination**

Sample size estimates assume 80% power and a two-sided alpha of 0.05 for cross-sectional stepped wedge studies comparing intervention to usual care in two-group statistical analyses. This method incorporates information on the number of steps used in the stepped wedge design, the number of subjects per time period, and the degree of clustering via the intra-class correlation coefficient (ICC) to compute the design effect. A sample size of 220 subjects per

group in a log rank test will provide 80% power at a two-sided alpha of 0.05 to detect a difference in the proportion of subjects with treatment at time,  $t$ , of 81% in the intervention group compared to 70% in the usual care group, a level estimated from recent data from the clinical sites for the planned study.

This difference yields a hazard ratio of 1.75, a clinically meaningful effect size for time-to-treatment post-diagnosis. Based on our planned number of steps, enrollment per study period, and a reasonable ICC of 0.1, the design effect is 2.29. Thus, we will need to enroll and follow at least 1,008 subjects to provide 80% power for analysis of intervention effectiveness. Our planned sample size of 1,300 women will therefore provide more than adequate power to test our primary outcome.

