## 5 Study Design

### 5.1.1 Study design

We will conduct a randomized stepped wedge design. This pragmatic design involves a sequential, randomized roll-out of the intervention across 6 participating clinical sites over 3-month intervals or “steps”. Thus, each site receives the intervention. **Table 4** details this approach: 21-month full historical control period followed, sequential roll out of the intervention every 3 months over an 18-month period, then an additional 24 months of full study intervention. A 3-month wash-out period between the end of the historical control collection period and the beginning of the intervention roll-out period is designed to minimize subject crossover contamination. Subjects diagnosed with breast cancer during the washout periods will be excluded from analyses.

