**5.1.4.1 Table 6. Expected Recruitment Projections**

Sites	Control	Intervention	Total
Boston Medical Center (BMC)	224	224	448
Beth Israel Deaconess (BIDMC)	85	128	213
Brigham and Women's/ DFCI	156	104	260
Faulkner Hospital (BWFH)	58	108	166
Tufts Medical Center (TMC)	32	39	71
Massachusetts General Hospital (MGH)	78	64	142
Total	633	667	1300

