### 12.3 Statistical Methods

Given the randomized stepped wedge design, we will report our results according to CONSORT guidelines. Our comparative analyses between the intervention and usual care (control) groups will employ the intent-to-treat principle. We will generate descriptive statistics (means, standard deviations, quantiles for continuous variables; counts/percentages for categorical variables) and schematic plots.

We will compare the intervention and usual care groups on salient variables in order to assess balance in the distributions of these variables. Variables found to differ between the study groups will be further evaluated to assess their confounding effects of intervention vs. usual care differences on primary and secondary outcomes. Given the nature of the cluster randomization employed, we will employ statistical analytic methods that take the correlated nature of the data into account.

Our primary analysis will use multiple logistic regression models to compare the proportion of patients with *timely initiation of treatment* across study groups, adjusting for the influence of race, language barriers to care, insurance status (private vs public), and other covariates that may have a significant effect on the outcome and may be unbalanced across the two study groups.

- To examine heterogeneity in intervention effect, exploratory analyses using multiple logistic regression interaction models will examine whether the effect of the TRIP intervention vary by three covariates of interest:
  - patient race
  - patient preferred language
  - insurance status
- Study groups will also be compared on the secondary clinical outcome of *time to initiation of primary cancer treatment* (the number of days from diagnosis to start of treatment) through Kaplan-Meier survival curves (unadjusted analyses) and Cox proportional hazards regression models controlling for cancer site and other covariates (adjusted analysis).
- *Receipt of quality care* will be analyzed through logistic regression.

For the analysis of the rate of missed appointments, patients will differ on the number of scheduled appointments over the study period. The odds of missing an appointment will be analyzed through generalized estimating equation (GEE) logistic regression models for repeated measures (appointments within patient) dichotomous data.

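### Section 12.2 equates 70% v 81% treated with a hazard ratio of 1.75, but it is 1.38; whether 1,300 is adequate depends on the target effect, the primary outcome and a calendar-time term that 12.3 does not name

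*Combined protocol and SAP*

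**What the plan says.** Section 12.2 assumes 80% power and two-sided alpha 0.05, and describes a method for cross-sectional stepped-wedge studies that uses the number of steps, the subjects per period and the ICC. It then gives this chain:

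- "A sample size of 220 subjects per" group, by log-rank test, for 81% v 70% treated at time t. No value of t is given there.
- "This difference yields a hazard ratio of 1.75, a clinically meaningful effect size for time-to-treatment post-diagnosis".
- From the steps, "enrollment per study period, and a reasonable ICC of 0.1, the design effect is 2.29", hence at least 1,008 subjects.
- "Our planned sample size of 1,300 women will therefore provide more than adequate power to test our primary outcome".

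Section 4.2.1 makes time to initiation of treatment, in days, the primary outcome and says the study is powered on it. Section 12.3 instead makes logistic regression on timely initiation the primary analysis, "adjusting for the influence of race, language barriers to care, insurance status (private vs public), and other covariates", and lists time to initiation as secondary. It promises methods for correlated data but names no calendar-time or period term.

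Section 5.1.1 describes a "21-month full historical control period followed, sequential roll out of the intervention every 3 months over an 18-month period". Two more years follow in which all sites deliver the intervention. A three-month washout per site is left out of the analysis. Table 6 gives control and intervention counts by site, 633 and 667 in all.

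**The concern.** Section 12.2 gives two different effects as if they were one, so a reader cannot tell which the trial is meant to detect. The design effect that carries 440 to 1,008 rests on an enrolment per period that is not printed beside it.

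In this design every site moves from control to intervention as time passes. A model without calendar time attributes any secular trend in timely treatment to the intervention. A model with calendar time loses precision, and the loss depends on the form of the term. The statement that 1,300 is more than adequate therefore cannot be judged until the effect, the outcome and the time term are fixed. If the term is chosen after the data are seen, the options differ widely in power and in their exposure to bias.

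**Working it through.** **1. The hazard ratio.** Under proportional hazards, HR = ln(1 − 0.81)/ln(1 − 0.70) = ln 0.19/ln 0.30 = 1.38. For HR 1.75 the treated share would be 1 − 0.30^1.75 = 0.878, that is, 70% v 88%. The odds ratio for 70% v 81% is 1.83 and the risk ratio 1.16, so neither explains 1.75.

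**2. The 220 per group** (80% power, two-sided 0.05).

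| Target | Log-rank (Schoenfeld, Freedman) | Two proportions |
|---|---|---|
| 70% v 81%, HR 1.38, 75.5% events | 201, 205 | 239 |
| 70% v 88%, HR 1.75, 79% events | 64, 67 | 80 |

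No formula gives exactly 220, but 220 lies inside the first row's range and far from the second's. With 220 per group, power for 70% v 81% is 83% by log-rank and 77% on proportions. For HR 1.75 it would be 99.9% by log-rank.

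**3. The design effect.** The plan's multiplication reproduces: 440 × 2.29 = 1,007.6, or 1,008. Enrolment per period can be inferred from Table 6. Control share × 20, in Table 4 site order and taking the Brigham and Women's/DFCI row as the sixth site, is 6.99, 7.98, 9.01, 10.00, 10.99 and 12.00. That is even accrual over 20 analysed quarters, or 1,300/(6 × 20) = 10.83 women per site-quarter. The standard stepped-wedge formula, scaled to total N, with k = 6 steps, one period of n women per step, b baseline periods and ICC ρ = 0.1, is

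DE = (b + k) × [1 + ρ(kn + bn − 1)]/[1 + ρ(kn/2 + bn − 1)] × 3(1 − ρ)/[2(k − 1/k)].

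- b = 1, n = 10.83: 7 × (8.481/5.232) × 0.2314 = 2.63, so 440 × 2.626 = 1,155. 1,300 still suffices.
- b = 7 (21 months), n = 10.83: 13 × (14.979/11.730) × 0.2314 = 3.84, so 440 × 3.842 = 1,690. 1,300 does not suffice.
- b = 1, n = 2.8: 2.29.

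The break-even design effect on the plan's 220 is 1,300/440 = 2.95.

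**4. Power on the planned layout.** The 21 + 18 + 24 months make 21 quarters. Each site has 7 to 12 control quarters, one excluded washout quarter and 13 to 8 intervention quarters, with Table 6 counts spread evenly and 1,300 analysed. In this layout 83% of women fall in quarters where all contributing sites are in the same arm. Generalised least squares with a random site effect and ICC 0.1 gives design effects, relative to an unclustered comparison of equal groups, of 0.92 (no time term), 3.95 (linear), 6.21 (year) and 8.25 (quarter).

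- Proportions: SE = √(DE × 4 × v/1,300), with v the mean of p(1 − p) over the two groups. For 70% v 81%, v = 0.182; with a linear term SE = 0.0470, and 0.11/0.0470 − 1.96 = 0.38, so power is 65%.
- Log-rank: events d = event share × 1,300/DE, and power = Φ(½ √d × ln HR − 1.96). Linear, to t: d = 0.755 × 329 = 248, so power is 72%.

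| Analysis | No term | Linear | Year | Quarter |
|---|---|---|---|---|
| 70% v 81%, proportions (12.3) | >99% | 65% | 46% | 37% |
| 70% v 81%, log-rank cut off at t | >99% | 72% | 52% | 42% |
| 70% v 81%, time to event, 97% eventually treated (assumed) | >99% | 82% | 63% | 51% |
| 70% v 88%, proportions | >99% | 98% | 91% | 81% |

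The minimum detectable difference from 70%, on proportions, is 13, 16 and 18 points for linear, year and quarter terms. A simulated logistic model with site terms (1,000 runs) gave 59%, 43% and 33% for 70% v 81%, and 97%, 84% and 72% for 70% v 88%.

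Other readings of the control window and washout give, for 70% v 81% on proportions, 62–71%, 45–62% and 36–53%. ICCs of 0.01 to 0.2 on the main layout give 61–69%, 43–50% and 34–40%.

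**5. No time term.** The documents give no secular trend, so any size of bias is an assumption. In 2,000 simulated trials with no true effect and an assumed yearly rise of 5%, 10% or 15% in the odds of timely treatment, the false-positive rate was 19%, 55% or 87% without a time term, and 5–6% with a linear one. With no drift and no time term it was 6%.

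**The case against.** The strongest reply is that the hazard ratio is only a label: 440 × 2.29 does not use it, and taking 2.29 at face value 1,300 gives 86–91% power for 70% v 81%. That stands as far as the multiplication goes, but the design effect is the weak link.

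Several stronger readings are tempting and should not be drawn:

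- *Power falls below 80% however calendar time is modelled.* This is too broad. Section 4.2.1 makes the time-to-event outcome primary and powered, and section 5.1.6 collects treatment through 12 months, so events may continue past t. With a linear term, power is then 79% if 90% are eventually treated and 81–83% at 95–100% (all assumed). A log-rank analysis to t also reaches 82–83% at ICC 0.2 with a linear term and the washout ignored.
- *The power statement rests on no model.* Section 12.2 cites a stepped-wedge method, and 2.29 is well above the 0.92 found without a time term, so it may already allow for period effects. The gap is that 12.3 names no matching term.
- *Calendar time is ruled out of 12.3.* It is not. The open-ended covariate clause could admit it, but it is not named.
- *The percentages were entered as shares not yet treated.* With the printed 70% and 81% that gives HR 1.69, not 1.75. Reaching 220 needs about 81.5%, which the plan does not print.

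**Conclusion.** The hazard ratio is wrong as written: 70% v 81% is 1.38, and 1.75 is 70% v 88%. This needs only proportional hazards. The 220 per group points to 70% v 81% as the working target, without proving it.

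The adequacy claim is conditional. For 70% v 81% at ICC 0.1, power is below 80% under all three time terms for the 12.3 binary analysis and for a log-rank cut off at t. For time to event with follow-up past t, it is about 82% with a linear term but below 80% on the main layout with year or quarter terms. For 70% v 88%, power is mostly adequate: about 80–98% on proportions by normal approximation, and about 72% in simulation with quarter effects. With only six sites, a t reference with 4 degrees of freedom lowers the quarter-effects figure to 57–73%.

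A reader might infer that the trial must enrol more women. The documents do not support that, because the answer turns on choices they leave open. The percentages rest on the layout inferred from Tables 4 and 6, even accrual and a constant site effect. The size of any secular-trend bias is unknown.

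**What to change.** Keep the sample size and make these changes.

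- **Target (12.2).** State which effect is intended, and correct either the hazard ratio to 1.38 or the proportions to 70% v 88%.
- **Outcome.** Reconcile section 4.2.1 with section 12.3 on which outcome is primary and powered.
- **Power (12.2).** Replace the design effect, the 1,008 and the adequacy sentence with power and minimum detectable difference for that target and analysis, computed from the site-by-quarter layout. Print enrolment per period, exclude the washout, show a range of ICCs, and reconcile the control window between the Protocol Summary (24 months before each site's start) and section 5.1.1.
- **Model (12.3).** Name the same calendar-time term in the primary model, before outcomes are analysed.

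The cost is a rewritten paragraph in 12.2, one stated term in 12.3 and the two reconciliations. No extra patients are needed and care does not change. The stated power may be less favourable, and the confidence interval will be wider.
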